## 7.3. Pharmacokinetic/Pharmacodynamic Relationships

Pharmacokinetic/pharmacodynamic modeling may be performed, including exploring the relationship between serum concentrations of daratumumab and endpoints of clinical efficacy and safety. If performed, details and results of the analysis will be presented in a separate report.

## 8. BIOMARKERS

Biomarker studies are designed to evaluate if there are any differences in depth of response, cytogenetic risk factors and immune-phenotypes in high risk SMM patients. Samples for biomarker evaluations will be collected as specified in the protocol Time and Events Schedule for bone marrow aspirate samples and whole blood samples.

With the emergence of highly effective drug regimens for multiple myeloma that effectively eliminate malignant plasma cells, the utility of assessing minimal residual disease (MRD) has gained greater importance in determining the depth of response to therapy. For this study, three threshold values,  $10^{-4}$ ,  $10^{-5}$  and  $10^{-6}$ , may be used to evaluate MRD negativity status and its predictive value for PFS and OS. The MRD negative rate will be calculated for the Daratumumab treatment group and the corresponding 95% exact CI will be provided.

A portion of the bone marrow aspirate samples collected, as specified in the Time and Events Schedule, will be utilized for translocation/mutation/genomic analysis (DNA/RNA) to assess whether specific molecular subgroups are responsive to daratumumab treatment. The high risk molecular subgroup is defined as subjects who have either del17p, t(4;14), t(14; 16), amp1q or a combination of these. This definition of high risk may evolve with emerging data from the scientific community. The standard-risk molecular subgroup includes subjects who had molecular test results by bone marrow aspirate, but do not meet molecular high-risk criteria. Analyses will evaluate ORR, PFS and OS as it relates to risk within each arm to see if they have similar outcomes to standard risk patients.

Biomarker studies are designed to identify markers predictive of response (or resistance) to daratumumab. Exploratory analyses, stratified by clinical covariates or molecular subgroups, may

be performed using the appropriate statistical methods (eg, parametric or non-parametric, univariate or multivariate, analysis of variance, or survival analysis, depending on the endpoint).

Subjects may be grouped by cohort, dose schedule, or clinical response. As this is an open-label study with an active monitoring control arm, statistical analyses will be done to aid in the understanding of the results.

Results of exploratory biomarker and pharmacodynamic analyses may be presented in a separate report. Planned analyses are based on the availability of clinically valid assays and may be deferred if emerging study data show no likelihood of providing useful scientific information.

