2. OBJECTIVES, ENDPOINTS, AND HYPOTHESIS

2.1. Objectives and Endpoints

2.1.1. Objectives

Primary Objective

The primary objective is to determine whether treatment with daratumumab administered SC prolongs PFS compared with active monitoring in subjects with high-risk SMM.

Secondary Objectives

- To demonstrate additional clinical benefit (ORR, duration of response, OS, etc) for subjects with high-risk SMM treated with daratumumab compared with active monitoring
- To assess the safety profile of daratumumab in subjects with high-risk SMM

- To assess the clinical characteristics of symptomatic MM following progression of disease after therapy with daratumumab
- To evaluate the PK and immunogenicity of daratumumab administered SC in subjects with high-risk SMM
- To evaluate the immunogenicity of rHuPH20 when administered in combination with daratumumab SC in subjects with high-risk SMM
- To evaluate the effect of treatment with daratumumab on health-related quality of life (HRQoL)

Exploratory Objectives

- To investigate clinical efficacy of daratumumab in high-risk subjects with genetic modifications (del17p, t(4:14), 1q gain, or other high-risk molecular subtypes)
- To explore biomarkers of response or resistance to daratumumab, including immunophenotypes and expression of MM markers (ie, CD38)

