9.4. Biomarkers

Per protocol Amendment 6, biomarker assessments by central laboratory will be discontinued.

Biomarker assessments will focus on 3 main objectives: determining the clinical benefit (ORR, PFS, and OS) of daratumumab in subjects with genetic modifications (del(17p13), amp(1q21), t(4;14), t(14;16), or other risk-associated molecular subtypes), depth of response by the absence of MRD, and to evaluate the immunophenotype of subjects with SMM for potential immune cell contributions to daratumumab response. All biomarker assessments will be performed centrally.

Bone marrow aspirates may be collected at screening and following treatment as outlined in the Time and Events Schedule. Bone marrow aspirates may be used for DNA/RNA sequencing in subjects with genetic modifications (del(17p13), amp(1q21), t(4;14), t(14;16), or other risk-associated molecular subtypes) and to monitor for potential predictive biomarkers of response or resistance such as changes in CD38, complement inhibitor protein expression, and changes in expression patterns of genes associated with ADCC, CDC, or other mechanisms of action of daratumumab.

In addition, baseline bone marrow aspirates may be subjected to DNA sequencing in order to establish the myeloma clone for MRD monitoring. A fresh bone marrow aspirate at Screening for all subjects is required, if possible, for MRD assessments. If a fresh bone marrow aspirate will not be performed at Screening because a sample is available within 56 days prior to randomization, then non-decalcified diagnostic tissue (bone marrow aspirate slides, touch-prep from biopsy [rolled biopsy] slides, or clot specimen slides) should be collected for MRD assessment. For subjects who achieve a sCR or CR, additional bone marrow aspirate may be used for assessment of MRD by next generation sequencing (NGS) of immunoglobulin heavy and light chains (Vij 2014³⁵). For subjects that maintain a sCR/CR, MRD may also be assessed at 12 months after date of initial sCR/CR in bone marrow aspirate. All MRD samples will be stored and analyzed if ORR data support testing. If this methodology is unavailable, or determined to be scientifically inferior, then alternative methods for MRD assessment may be utilized. In cases where daratumumab is suspected of interfering with SIFE and preventing determination of CR, subjects with VGPR may also be evaluated for MRD by NGS.

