11.6. Biomarker Analyses

Biomarker studies are designed to identify markers predictive of response (or resistance) to daratumumab. Analyses will be stratified by clinical covariates or molecular subgroups using the appropriate statistical methods (eg, parametric or non-parametric, univariate or multivariate, analysis of variance, or survival analysis, depending on the endpoint). Correlation of baseline expression levels or changes in expression levels with response to time-to-event endpoints will identify responsive (or resistant) subgroups in addition to genes and pathways attenuated following treatment with daratumumab.

Any pharmacodynamic measures will be listed, tabulated, and where appropriate, plotted. Subjects may be grouped by cohort, dose schedule, or clinical response. As this is an open-label study with an active monitoring control arm, statistical analyses will be done to aid in the understanding of the results.

Results of biomarker and pharmacodynamic analyses may be presented in a separate report. Planned analyses are based on the availability of clinically valid assays and may be deferred if emerging study data show no likelihood of providing useful scientific information.

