### 1.1. Trial Objectives

The primary objective of this study is to determine whether treatment with daratumumab SC prolongs progression-free survival (PFS) compared with active monitoring in subjects with high-risk SMM.

The secondary objectives are as follows:

- To demonstrate additional clinical benefit (ORR, duration of response, OS, etc) for subjects with high-risk SMM treated with daratumumab compared with active monitoring
- To assess the safety profile of daratumumab in subjects with high-risk SMM
- To assess the clinical characteristics of symptomatic MM following progression of disease after therapy with daratumumab
- To evaluate the pharmacokinetics and immunogenicity of daratumumab administered SC in subjects with high-risk SMM
- To evaluate the immunogenicity of recombinant human hyaluronidase (rHuPH20)
- To evaluate the effect of treatment with daratumumab on patient-reported outcomes

The two exploratory objectives are as follows:

- To investigate clinical efficacy of daratumumab in high-risk subjects with genetic modifications (del17p, t(4:14), 1q gain, or other high-risk molecular subtypes)
- To explore biomarkers of response or resistance to daratumumab, including immunophenotypes and expression of MM markers (ie, CD38)

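### SAP Section 8 aims at predictive molecular markers, but its only named contrast is high versus standard risk within each arm, with no treatment-by-marker interaction estimate

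*SAP*

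**What the plan says.** The aim concerns treatment effect. The exploratory objective in Protocol 2.1.1 reads "To investigate clinical efficacy of daratumumab in high-risk subjects with genetic modifications", and SAP 1.1 repeats it. Protocol 9.4 restates it as "determining the clinical benefit (ORR, PFS, and OS) of daratumumab in subjects with genetic modifications". SAP Section 8 adds: "Biomarker studies are designed to identify markers predictive of response (or resistance) to daratumumab".

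The method is less direct. SAP Section 8 first defines its group: "The high risk molecular subgroup is defined as subjects who have either del17p, t(4;14), t(14; 16), amp1q or a combination of these". It allows this definition to change as outside data emerge. The analysis it then names is "ORR, PFS and OS as it relates to risk within each arm to see if they have similar outcomes" to those of standard-risk subjects. Further exploratory analyses by molecular subgroup are allowed, with the statistical method left open.

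Protocol 11.6 also leaves methods open. The one route it names to responsive subgroups is correlation: "Correlation of baseline expression levels or changes in expression levels with response to time-to-event endpoints will identify responsive (or resistant) subgroups".

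Two other places bear on the point:

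- SAP 2.4 and Table 3 list cytogenetic risk at study entry (yes/no, the same four lesions) as a PFS subgroup. SAP 5.2.2 gives the between-arm hazard ratio as the PFS summary measure.
- SAP Attachment 1 carries the Section 2.4 subgroups over to PFS, ORR, PFS2, OS and other endpoints, on condition that the data warrant it.

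Neither document specifies a treatment-by-marker interaction.

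**The concern.** A marker is predictive if the effect of daratumumab against active monitoring differs between marker-positive and marker-negative subjects. A comparison of high-risk with standard-risk subjects inside the daratumumab arm does not isolate that difference. It also carries whatever the marker does to prognosis without treatment.

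Two misreadings follow if the daratumumab-arm contrast is read by itself. A marker that is only prognostic can be reported as a resistance marker. A real difference in benefit can be hidden when it offsets poor prognosis, because the two risk groups then look alike.

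The similarity criterion adds a second problem. Section 8 states no margin, and failing to find a difference in a small subgroup does not show that outcomes are similar.

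**Working it through.** **Plan's own figure.** SAP 1.4 gives 165 PFS events, HR 0.625, two-sided 5% and 85% power. By Schoenfeld's formula with 1:1 allocation, power = Φ(√165/2 × ln(1/0.625) − 1.96) = Φ(3.02 − 1.96) = 85.5%. The figure reproduces, so the same approximation is used below.

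**What the within-arm contrast measures.** Let g be the high- versus standard-risk HR under active monitoring (prognosis). Let r be the treatment HR in high-risk subjects divided by the treatment HR in standard-risk subjects (effect modification). Under proportional hazards:

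- active monitoring arm: contrast = g
- daratumumab arm: contrast = g × r
- ratio of the two contrasts = r, the interaction

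The values of g and r below are hypothetical. The standard-risk treatment HR is the design value, 0.625.

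| g | Treatment HR, high risk | r | Monitoring arm | Daratumumab arm |
|---|---|---|---|---|
| 2 | 0.625 | 1.0 | 2.0 | 2.0 |
| 2 | 0.31 | 0.5 | 2.0 | 1.0 |
| 1.5 | 1.0 | 1.6 | 1.5 | 2.4 |

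Row 1 has equal relative benefit, but the daratumumab arm shows a twofold gap. Row 2 has a much larger benefit in high-risk subjects, but the daratumumab arm shows no gap. Row 3 has no benefit in high-risk subjects; the 2.4 mixes prognosis (1.5) with effect modification (1.6). In no row does the daratumumab-arm figure give the daratumumab versus monitoring HR in high-risk subjects.

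**Illustration with cited medians.** Protocol 3.2 cites times to progression of 28 months for t(4;14) and 55 months for t(11;14). Assuming exponential times, g = 55/28 = 1.96.

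- Treatment HR 0.625 in both groups: medians 28/0.625 = 44.8 and 55/0.625 = 88.0 months, so the daratumumab-arm contrast is 88.0/44.8 = 1.96 although r = 1.
- Treatment HR 0.5 (hypothetical) in t(4;14) and 1.0 in t(11;14): medians 28/0.5 = 56 and 55 months, so the contrast is 55/56 = 0.98 although r = 0.5.

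This is illustrative only. The SAP's standard-risk group is everyone tested without a high-risk lesion, not t(11;14).

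**Precision of the alternative.** The documents give no marker prevalence. Assume the high-risk group supplies 20-50% of the 165 PFS events, with events split about equally between arms. With e events in high-risk subjects, SE(log HR) = √(4/e) and SE(log interaction) = √(4/e + 4/(165 − e)).

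| Assumed share | e | 95% CI around HR 0.625 | Subgroup power, HR 0.625 | Interaction power, ratio 1.6 | Ratio detectable at 80% power |
|---|---|---|---|---|---|
| 20% | 33 | 0.32-1.24 | 27% | 23% | 2.98 |
| 50% | 82.5 | 0.41-0.96 | 57% | 33% | 2.39 |

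For the 20% row, SE = √(4/33 + 4/132) = 0.389 and power = Φ(0.470/0.389 − 1.96) = Φ(−0.75) = 23%. A ratio of 1.6 corresponds to a treatment HR of 0.625 in standard risk and 1.0 in high risk. OS, with 107 events expected at study end, would be less precise.

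**The case against.** The strongest reply is that the plan as a whole does more than Section 8, and much of that stands.

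- A reader might infer that the objective on high-risk genetics goes unanswered. The documents do not support this. Table 3 plans PFS by cytogenetic risk using the same four lesions, and the PFS effect measure is the between-arm HR.
- A reader might infer that OS and ORR are examined only within arms. Attachment 1 extends the same subgroups to both, although conditionally and as exploratory support.
- A reader might infer that the untreated arm is ignored. Section 8 makes the contrast in each arm. Set side by side, the pairs 2.0 and 2.0, or 2.0 and 1.0, would point an alert reader the right way. What is missing is any plan to form their ratio or attach an interval.
- The within-arm contrast has a use. Protocol 3.2 expresses interest in how these abnormalities contribute to progression. For ORR, if responses under monitoring are near zero (an assumption), the daratumumab-arm contrast bears on responsiveness directly.
- The analysis is exploratory, may be deferred or reported separately, and lies outside the testing hierarchy. With 23-33% power for a ratio of 1.6, an interaction estimate would rarely settle a question.

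These points lower the severity but leave the mismatch. Table 3 and Attachment 1 use one composite FISH variable, so they do not separate del(17p), t(4;14) and 1q gain and do not reach sequencing or expression markers. Section 8 cross-refers to neither, and its definition of high risk may drift from Table 3.

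**Conclusion.** The concern holds as a low-severity, exploratory point: the contrast named in SAP Section 8 does not match the section's stated aim. In the daratumumab arm it equals prognosis times effect modification, so by itself it cannot show differential benefit, and a non-significant difference does not establish similarity. No interaction estimate is planned for any marker. Individual lesions and sequencing or expression markers have only open-ended methods and, in Protocol 11.6, correlation.

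It does not follow that the efficacy objective in high-risk genetics is unaddressed, or that the primary or hierarchical conclusions are affected.

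The algebra rests on proportional hazards. The values of g and r are hypothetical, and the precision figures rest on the assumed 20-50% event share.

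**What to change.** In SAP Section 8:

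1. Keep the within-arm contrasts, label them prognostic or descriptive, and drop the reading of similar outcomes.
2. For each baseline marker with data in both arms, give the daratumumab versus active monitoring HR with 95% CI for PFS and OS within marker-positive and marker-negative subjects.
3. Add the treatment-by-marker interaction (ratio of HRs) with 95% CI, from a Cox model stratified by number of risk factors (<3 vs ≥3).
4. Cross-refer to Table 3 and Attachment 1, so that the composite high-risk definition is the same throughout.
5. Apply the same approach to the baseline markers in Protocol 11.6. On-treatment changes in expression are not baseline variables and should stay descriptive.

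Present all of this as exploratory estimation, without declaring markers predictive on significance alone. Protocol Amendment 6 records that the primary analysis has concluded, so analyses added now should be labeled post hoc.

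The cost is SAP wording and a few extra models on data already collected. Sequencing is optional under Protocol 9.4, so some markers may lack data in both arms and would be left out. The drawback is wide intervals, as shown above, so fewer markers will be called predictive.

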## **9. PATIENT-REPORTED OUTCOMES**

Patient-reported outcomes (PROs) will be evaluated in this study through the following 3 instruments: EORTC QLQ-C30, EORTC QLQ-MY20, and the EQ-5D-5L. The EORTC QLQ-C30, EORTC QLQ-MY20, and the EQ-5D-5L will be scored based on the instrument developer guidelines. No imputation will be done for the PRO data.

The EORTC QLQ-C30 includes 30 items resulting in 5 functional scales (physical functioning, role functioning, emotional functioning, cognitive functioning, and social functioning), 1 global health status scale, 3 symptom scales (fatigue, nausea and vomiting, and pain), and 6 single items (dyspnea, insomnia, appetite loss, constipation, diarrhea, and financial difficulties). The recall period is 1 week (the past week). A higher score represents a higher (“better”) level of functioning, or a higher (“worse”) level of symptoms. The EORTC QLQ-MY20 is a disease-specific module administered with the EORTC QLQ-C30 in patients with multiple myeloma. From the EORTC QLQ-MY20, 9 items were administered resulting in the disease symptom scale and the future perspective scale. The recall period, response options, and score interpretation are the same as the EORTC QLQ-C30.

The EQ-5D-5L is a generic measure of health status. The EQ-5D-5L is a 5-item questionnaire that assesses 5 domains including mobility, self-care, usual activities, pain/discomfort and anxiety/depression plus a visual analog scale rating “health today” with anchors ranging from 0 (worst imaginable health state) to 100 (best imaginable health state). The scores for the 5 separate questions are categorical and cannot be analyzed as cardinal numbers. However, the scores for the 5 dimensions are used to compute a single utility score ranging from zero (0.0) to 1 (1.0) representing the general health status of the individual (but scoring by the UK algorithm allows for values less than 0).

Analysis of PRO data will be performed on ITT analysis set. For subjects with multiple records at the same visit, the closest one to the visit date will be selected as the scheduled assessment.

At each time point for analysis, the number and percentage of PRO instrument assessment forms that are expected, received, and missing will be tabulated by treatment group. The missing PRO assessments are defined as the expected number of assessments for a visit minus the actual number of assessments received for that visit, the expected number of assessments per visit will be determined by subject-level study completion status.

## **9.1. Patient Reported Outcome Endpoints**

The PRO endpoints are secondary and not part of the statistical hierarchy. Type I error control will not be applied to PRO data.

### **9.1.1.1. Definition**

Key PRO Endpoints

- EORTC QLQ-C30: global health status (GHS); emotional functioning
- EORTC QLQ-MY20: Future perspective
- EQ-5D-5L: utility values and visual analog scale (VAS)

### **9.1.1.2. Analysis Method**

Descriptive statistics (n, mean, standard deviation, median, and range) will be provided for all PRO endpoints at each time point, by treatment group.

A repeated measures mixed effects model analysis will be conducted estimating change from baseline at each time point between two treatment groups. ITT subjects who have a baseline value and at least one post-baseline value are included in the analysis. Change from baseline will be fitted to a mixed effects model including subjects as a random effect, and baseline value, treatment group, time in month, treatment-by-time interaction, and the stratification factor as fixed effects. Line plot of LS mean change from baseline, with standard error, over time may be displayed by treatment group.

## **9.1.2. Time to worsening/improvement**

### **9.1.2.1. Definition**

For the key PRO endpoints, time to worsening and time to improvement will be derived. A distribution based method will be used to define worsening/improvement in scores, i.e., half standard deviation away from the mean score at baseline combining both treatment groups.

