PRO endpoints are to be assessed during the screening window, the Active Monitoring/study treatment phase, during pre-PD follow-up, at the time of disease progression, and during post-PD phases. PRO data collection during the Screening Phase will serve as the baseline score, to be collected after the subject signs informed consent. PRO assessments should be administered prior to any interventions that could influence subject perceptions of their health state, scheduled for the same day as PRO assessments are collected. The goal of data collection during the Active Monitoring/study treatment phase is to measure changes in emotional functioning due to receiving or not receiving treatment and to measure the impact of adverse events from daratumumab treatment on HRQoL. The goal of data collection during the pre-PD phase is to measure HRQoL after treatment and the value of potentially being in a pre-PD state longer because of treatment. The goal of data collection during the post-PD phase is to measure the onset and severity of symptoms associated with MM. Subject burden related to completion of PRO measures was a key consideration in determining the number of assessments as well as the timepoints likely to observe potential change in scores. If no in-person visit is scheduled, PROs can be interviewer-administered during tele-health (conducted via phone or video conference) visits.

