### **9.1.2.2. Analysis Method**

Time to worsening will be estimated using Kaplan-Meier methods. The hazard ratio for daratumumab relative to active monitoring and its associated 95% confidence interval (CI) will be calculated based on the stratified Cox proportional hazards model by the stratification factor at the randomization. Death due to disease progression will be considered as worsening. Subjects who have not met the definition of worsening will be censored at the last PRO assessment. Subjects without baseline assessment or post-baseline assessment will be censored at date of randomization.

Time to improvement will be summarized using descriptive statistics such as mean, standard deviation (SD), median and range.

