**2. ENDPOINTS FOR SUBGROUP ANALYZES**

As described in Sections 5.2 (Primary Efficacy Endpoints), 5.3 (Secondary Endpoints) and 9.1 (Patient-Reported Outcomes), the following endpoints will be evaluated by subgroups as defined in Section 1, Appendix:

- PFS
- Time to Biochemical or SLiM-CRAB progression
- ORR
- Time to first-line treatment for MM
- PFS2
- OS
- Duration of response
- Time to Response
- EORTC QLQ-C30, EORTC QLQ-MY20, EQ-5D-5L (Section 9.1.1.1)
- PRO: Time to worsening/improvement (Section 9.1.1.2)
- Time to progression
- Incidence of MM with adverse prognostic features

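### SAP 9.1.2.1 defines PRO worsening and improvement by distance from the pooled baseline mean and omits the subject's own baseline; SAP 9.1.2.2 summarizes time to improvement without accounting for subjects who do not improve

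*SAP*

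**What the plan says.** **Event definition.** SAP 9.1.2.1 derives time to worsening and time to improvement for the key PRO endpoints: global health status, emotional functioning, future perspective, and EQ-5D-5L utility and VAS. It uses a distribution-based rule, a score "half standard deviation away from the mean score at baseline combining both treatment groups".

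**Time to worsening.** SAP 9.1.2.2 gives Kaplan-Meier estimates and a stratified Cox hazard ratio with 95% CI, and counts death due to progression as worsening. On censoring it says: "Subjects who have not met the definition of worsening will be censored at the last PRO assessment". It adds: "Subjects without baseline assessment or post-baseline assessment will be censored at date of randomization".

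**Time to improvement.** SAP 9.1.2.2 has one sentence: "Time to improvement will be summarized using descriptive statistics such as mean, standard deviation (SD), median and range".

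**Related text.** Protocol 9.5 says that "PRO data collection during the Screening Phase will serve as the baseline score". Protocol 2.1.2 defines the PRO endpoints as change from baseline, and Protocol 11.8 analyses them that way. SAP 9.1.1.2 does the same: "Change from baseline will be fitted to a mixed effects model including subjects as a random effect". SAP Attachment 1 plans time to worsening/improvement by subgroup but cites Section 9.1.1.2, the mixed-model section. SAP 9.1 places all PRO endpoints outside the testing hierarchy.

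**The concern.** As written, the reference point is a group mean. Each scale then has two fixed score values, half an SD below and half an SD above the pooled baseline mean, and a subject's event status depends on where the later score lies, not on how far it has moved. A subject who enters with a low score and stays there can be recorded as worsened at the first post-baseline visit. A subject who falls a long way from a high starting score may not be recorded at all.

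The usual within-subject rule would give a different set of events from the same data. A hazard ratio is planned for worsening, in an open-label trial, so a reader needs to know which rule produced it.

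The gap for improvement is separate. A mean, SD, median and range of observed times describe only those who improved. They carry no information on how many did not, and they do not handle incomplete follow-up.

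**Working it through.** The documents state no PRO means, SDs, correlations or improvement rates, so there is no figure of the plan's own to reproduce. Everything numerical below rests on stated assumptions.

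**1. Which reading does the text support?** The definition itself names only the pooled mean. Three things point to a within-subject rule:
- Subjects without a baseline score are censored at randomization, which a fixed cut-off would not need.
- A baseline score is collected from every subject.
- The other between-arm PRO analyses use change from baseline.

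No place in either document states the own-baseline rule for this endpoint, and the Attachment 1 pointer leads to a section with no definition of worsening.

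**2. Subjects past the literal line at baseline.** Assume normal scores, standardized on the pooled baseline mean and SD. P(X < -0.5) = Φ(-0.5) = 0.3085, or 30.9%. With about 360 subjects, 360 × 0.3085 ≈ 111. By symmetry another 30.9% start past the improvement line. With no true change and a correlation r between visits of 0.5 to 0.8, 53% to 71% of subjects who start past the worsening line are also past it at the first later visit.

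**3. Disagreement between the two rules at one visit.** X is the baseline score, Y the later score, and there is no true change. The fixed rule is Y < -0.5 and the own-baseline rule is Y - X < -0.5. With s = √(2(1-r)), P(own) = Φ(-0.5/s) and corr(Y, Y-X) = (1-r)/s. The disagreement is P(fixed) + P(own) - 2P(both).

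| r | P(fixed) | P(own) | P(both) | Classified differently |
|---|---|---|---|---|
| 0.5 | 0.3085 | 0.3085 | 0.1633 | 29.0% |
| 0.6 | 0.3085 | 0.2881 | 0.1474 | 30.2% |
| 0.7 | 0.3085 | 0.2593 | 0.1277 | 31.2% |
| 0.8 | 0.3085 | 0.2146 | 0.1010 | 32.1% |

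**4. The same over five visits.** Simulation of 1,000,000 subjects with equal correlation between all visits and no true change; an event is the first crossing at any visit.

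| r | Fixed rule | Own-baseline rule | Classified differently |
|---|---|---|---|
| 0.5 | 65% | 65% | 37% |
| 0.6 | 60% | 62% | 40% |
| 0.7 | 56% | 58% | 42% |
| 0.8 | 51% | 51% | 44% |

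Over five visits the two rules produce about the same number of chance events, but in different subjects.

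**5. Time to improvement.** PRO visits follow Protocol Table 1: Weeks 12, 24 and 60, then yearly, taken as Weeks 112 and 164. The end-of-treatment and progression assessments are left out for simplicity. Follow-up is taken as uniform over 24 to 48 months, from the 24-month accrual plus 24-month follow-up in Protocol 11.2. Improvement times are assumed exponential. Week 164 is 37.7 months, so improvement by then, which Kaplan-Meier estimates, is 1 - 2^(-37.7/median). Week 60 is 13.8 months.

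| Assumed true median | Observed to improve | Improver-only median | Improver-only mean | Improved by Week 164 |
|---|---|---|---|---|
| 24 months | 57% | Week 60 | 17.6 months | 66% |
| 36 months | 43% | Week 60 | 18.5 months | 52% |
| 60 months | 29% | Week 60 | 19.3 months | 35% |

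The share improving by Week 164 falls by almost half (66% to 35%), while the improver-only median does not move and the mean moves by 1.7 months (19.3 - 17.6).

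**The case against.** **Intent.** The literal reading is probably not what was meant. Worsening and improvement are words of change, and the baseline-censoring sentence has no purpose under a fixed cut-off. This stands: the first part is an incomplete definition, and a reader should not infer that the sponsor deliberately chose a population cut-off. But the sentence is introduced as the definition, and it names a different reference point from the one apparently intended.

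**Convention.** SAP 5.3.9.2 summarizes time to response among responders by the same statistics, and the sentence on improvement leaves room for others to be added. No test or hazard ratio is planned for improvement. This also stands: an improver-only description follows the SAP's own pattern. Unlike SAP 5.3.9.2, though, SAP 9.1.2.2 does not name the population, and for improvement it does not commit to reporting how many improve.

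**Assumptions.** Normality is doubtful in asymptomatic subjects and for a scale built from three questions. The 30.9% is therefore an illustration; skewed or bounded scores would change it.

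**Stronger readings that a reader might infer.**
- That the literal rule biases the comparison between arms. The documents give no ground for this: the same line applies to both randomized arms. Which rule is more sensitive to a real difference depends on a correlation that is not given.
- That the own-baseline rule is less prone to chance events. At one visit it is when r exceeds 0.5, but over five visits the two are about equal. The case for it is clarity of meaning.
- That unequal follow-up between arms would by itself distort the improvement medians. This depends on assumed post-progression PRO collection, and with scheduled visits the median can fall only on a visit week. No such effect is claimed.

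**Conclusion.** The point holds as a gap in definition and summary, of low severity. The only written definition of PRO worsening and improvement leaves out the subject's own baseline. The literal and the apparently intended rules would classify about 29% to 32% of subjects differently at one visit and 37% to 44% over five, assuming normal scores, no true change and r from 0.5 to 0.8. The planned description of time to improvement can look the same when the proportions improving are far apart, under exponential times and the scheduled visits.

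The reach is narrow. Time to worsening/improvement is not listed among the endpoints in Protocol 2.1.2, and PROs carry no type I error control. PFS and the mixed-model PRO analysis are untouched. The rationale for protocol Amendment 6 says that the primary analysis has concluded and the study was unblinded, so a new rule can no longer count as fixed in advance; disclosure is what remains.

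**What to change.** - In SAP 9.1.2.1, define worsening (improvement) as a change of at least 0.5 × the pooled baseline SD from the subject's own baseline, in the worse (better) direction. It would help to say how subjects too close to a scale limit to meet the rule are handled.
- In SAP 9.1.2.2, estimate time to improvement by Kaplan-Meier, censor subjects who do not improve at their last PRO assessment, and report the number and percentage improving by arm. A Cox comparison is optional.
- In Attachment 1, correct the cross-reference for time to worsening/improvement to Section 9.1.2.
- State in the study report which rule was programmed for the primary analysis. If it was the literal one, report the own-baseline rule beside it as a sensitivity analysis and label it as specified after unblinding.

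The cost is a few lines of SAP wording, derivation code and one set of additional tables. No new data are needed.
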